3.4 Exclusion Criteria

Protocol/Amendment No.: RETRO STUDY, v0.3

VEAP ID NO: 7651

1) Patients co-infected with HIV-2. (A diagnosis of HIV-2, a positive HIV-1/HIV-2 Multispot, a positive HIV-2-specific ELISA and/or a positive HIV-2 Western Blot will all be considered evidence of HIV-2 coinfection.)

2) Patients who initiated RAL OD or other ART as part of a clinical trial.

4 Variables and Epidemiological Measurements

4.1 Exposure

Subjects treated with RAL OD will be identified by the administering clinicians within the treatment centres. Unless they discontinue treatment during the study period, subjects will have been taking RAL OD for at least 6 months.

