RAL BID has the longest post-marketing experience of the INSTI class; both clinical trials and clinical experience have demonstrated durable virologic suppression in treatment-naïve and treatment-experienced patients, including patients with extensive antiretroviral experience and documented antiretroviral resistance. (7) A new 1200 mg, once-daily formulation of RAL (RAL OD), administered orally as two 600 mg tablets, was found to have non-inferior efficacy compared to RAL BID in a randomised clinical trial of treatment naïve HIV-1 infected patients (ONCEMRK).(8) RAL OD gained Marketing Authorization in July 2017 and was first available for prescription in September 2017. Once-daily regimens are often preferred by both patients and clinicians in order to facilitate adherence and improve patient quality of life. The RAL OD formulation administers a higher daily dose of raltegravir, as compared to RAL BID, in order to sustain sufficient trough concentrations (8).

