3 METHODOLOGY

3.1 Summary of Study Design

This is a non-interventional, retrospective observational chart review study at 2 UK treatment centres that will utilize electronic data capture (EDC) to address study objectives.

The study will capture data from 300 HIV-1 positive adult subjects receiving RAL OD as part of their ART at UK NHS treatment centres. NHS records generally capture all of the usual care of an HIV positive patient including their physical exams, diagnoses, laboratory findings, medication prescriptions, co-morbidities, social history and demographic data.

All eligible HIV-1 infected adult patients (\geq 18 years) who initiated RAL OD based ART from September 2017 will be included in this study on a sequential sampling basis. Data from eligible patients' medical charts will be extracted for the time of initiation and at 6 months (window of -1/+3 months) post-initiation follow up appointment.

The index ARV regimen is defined as the first RAL 1200mg OD (2 x 600mg) containing ARV regimen a patient receives and the baseline will be defined as the RAL 1200mg OD

Protocol/Amendment No.: RETRO STUDY, v0.3

VEAP ID NO: 7651

initiation prescription date. Treatment with RAL OD must have been initiated during or after September 2017 and before April 1st 2018 for the primary baseline data collection. Subjects should have at least one 6 month (-1/+3 months) follow up appointment before December 31st 2018 to ensure 6 month secondary outcomes data are available for analysis. Chart review will only be carried out once a patient has completed the 6 month visit to ensure all data are captured retrospectively.

This time period was selected based on expectations of RAL OD utilization over time in the post-launch period and standard UK practice of 6-monthly clinic appointments.

The final analysis will be conducted following database lock after the last study participant has reached the 6 (-1/+3) months treatment milestone, by December 31st^h 2018, and all data queries have been resolved.

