3.2 Study Population

The study will be conducted in 2 NHS hospital HIV departments in the UK. To ensure the data are representative of the UK, centres will be chosen to represent London and non-London in proportion with the treated patient population. As approximately 50% of UK HIV patients are treated in London, one of the potential sites will be selected from the largest treatment centres in London. The additional site will be a non-London treatment centre, and will be selected primarily based on the number of eligible patients treated.

Patients who were initiated on RAL OD at least 6 months ago will be identified by the clinician, Principal Investigator or a member of the clinical team, from review of hospital records and databases as appropriate at each centre. From a list of eligible patients with the required data, the earliest recent record will be recorded as the first participant and then all further eligible participants up to 150 per centre will be selected sequentially to minimize bias.

It is intended that approximately 150 patients will be included from each participating centre to represent a proportionate spread. Oversampling may be performed in the larger centre in order to maintain an overall sample size of 300.

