8.2 Bias

It is intended that data will be collected on consecutive patients in who at least 6 months follow-up was possible (i.e. started RAL OD during or after September 2017). Eligible patients must have completed their 6 month follow up before 31st December 2018. This will include any patients who may have moved treatment centres since initiation. Participating centres will be selected to be representative of the UK population, one site from within London (where approximately 50% of HIV patients in the UK are currently treated) and one from outside London will be used.

The study is a retrospective chart review study that will be using data extracted from databases; any missing data will be queried with the sites and if not available, will be recorded as such.

Any observational study has the possibility of residual confounding due to unknown risk factors [13]. However this study is designed to collect information on recent prescribing practice and is based on clinical experience and knowledge of the HIV physician.

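### No common, checkable source is fixed for listing RAL OD starters, so patients who stopped early may be under-listed relative to the stated all-initiator denominator

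*Protocol*

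**What the plan says.** Section 4.1 assigns identification to the treating side: "Subjects treated with RAL OD will be identified by the administering clinicians within the treatment centres". Section 3.2 widens who may do it and names the kind of source: patients are "identified by the clinician, Principal Investigator or a member of the clinical team, from review of hospital records and databases as appropriate at each centre".

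On timing, section 3.2 states "Patients who were initiated on RAL OD at least 6 months ago will be identified", and section 3.1 adds "Chart review will only be carried out once a patient has completed the 6 month visit". Selection then runs in date order down a list: "From a list of eligible patients with the required data, the earliest recent record will be recorded as the first participant". Sections 3.2 and 8.2.1 both present this sequential selection as the protection against bias.

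Section 4.1 expects some sampled patients to have discontinued. Section 2.2 lists the proportions still taking RAL OD and discontinuing it among the secondary objectives. Section 8.1.2 takes everyone who started RAL OD as the denominator for the secondary objective.

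**The concern.** Sequential selection protects against bias only if the list it runs down is complete, or at least equally complete for patients who stayed on the drug and patients who left it. The protocol does not secure this. The source may differ between the two centres, no completeness check is described, and the people compiling the list work at a time when the 6-month outcome may already be in the notes.

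If brief users of RAL OD are listed less often than continuing users, discontinuation is understated and persistence overstated. The baseline profile would also shift if stoppers differ from continuers at baseline. A later SAP cannot repair this: section 8 requires it only before database closure, and by then the sample has been drawn.

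**Working it through.** **1. What fixes the frame.** Setting the sections side by side:

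- Who lists: the administering clinicians (4.1); the clinician, the Principal Investigator or a team member (3.2).
- From what: records and databases, chosen by centre (3.2).
- When: at least 6 months after the start (3.2), with chart review after the 6-month visit (3.1).
- Completeness check, or count of starters against patients included: none described.
- Population the results refer to: all starters (8.1.2).

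**2. The plan's own figure.** 2 centres × 150 = 300, as stated in 3.2. Section 8.3 promises precise estimates but gives no precision target, so there is nothing further to reproduce.

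**3. Size of the possible bias.** Let d be the true 6-month discontinuation, s_d the share of stoppers listed and s_c the share of continuers listed. Then

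observed = d·s_d / [d·s_d + (1 − d)·s_c].

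The protocol gives none of these three quantities. I assume s_c = 0.98, s_d = 0.9, 0.8 or 0.6, and d = 15% or 20%. For example, with d = 0.15 and s_d = 0.6: 0.090 / (0.090 + 0.833) = 0.098.

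| True d | Stoppers listed | Observed | Bias (points) |
|---|---|---|---|
| 15% | 90% | 13.9% | −1.1 |
| 15% | 80% | 12.6% | −2.4 |
| 15% | 60% | 9.8% | −5.2 |
| 20% | 90% | 18.7% | −1.3 |
| 20% | 80% | 16.9% | −3.1 |
| 20% | 60% | 13.3% | −6.7 |

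If every listed patient is either on or off RAL OD at 6 months, persistence is the complement: a true 85% would be observed as 86.1% to 90.2%.

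**4. Against sampling error.** The 95% half-width is 1.96·√[p(1 − p)/300], which is 4.0 points at p = 15% and 4.5 points at p = 20%. The bias exceeds it only when 60% of stoppers are listed (5.2 against 4.0; 6.7 against 4.5). At 80% and 90% it lies inside.

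**5. What a better frame would and would not do.** If s_d = s_c, the formula returns d, so equal listing removes this bias. Three filters remain after listing: the completed 6-month visit (3.1, 8.2.1), availability of the required data (3.2), and wording in 8.2.1 that can be read as requiring six months or more on treatment. A stopper who still attends and has data passes the first two; one without a visit or data does not. On that reading of 8.2.1, no early stopper passes the third. This sits badly with 4.1, which expects discontinuers, and with 8.1.2, which counts all starters.

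**The case against.** The best defence is that the plan is already record-based. Section 3.2 requires review of records and databases. Section 3.1 aims to include all eligible starters, notes that NHS records generally hold prescriptions, and dates baseline from the initiating prescription. Section 8.2 keeps patients who have since moved centre. The centres were not yet selected, which is a reason to leave the source open. Outcomes are on record in any retrospective chart review, and date-ordered selection limits discretion. The affected proportions are secondary, and the study tests no hypothesis.

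Much of this stands, and it rules out several stronger readings that a reader might infer:

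- *That the list rests on clinicians' memory.* Section 3.2 says otherwise.
- *That 3.2 and 4.1 contradict each other.* Section 3.2 elaborates 4.1, and both can be followed together.
- *That section 8.2 confirms reliance on recall*, because it says the study "is based on clinical experience and knowledge of the HIV physician". That sentence concerns prescribing practice and residual confounding, not how patients are listed.
- *That a dispensing list would capture every starter.* Section 1.1 describes RAL OD as "administered orally as two 600 mg tablets" and RAL BID as 400 mg tablets, so tablet strength is a natural marker. Nothing shows that either centre holds a complete, searchable record of it.
- *That the bias is known to be large.* The documents give no listing rate.

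What the defence does not supply is a named source common to both centres, or any means of showing that the list is complete.

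**Conclusion.** The point holds as an inexpensive improvement to the design, not as a demonstrated error. The protocol fixes no common, verifiable frame for RAL OD starters, identifies them when outcomes may already be known, and describes no completeness check, while its persistence figures refer to all starters. If stoppers are listed less often than continuers, discontinuation is understated. The amount cannot be derived from the documents: under the assumed listing rates it runs from about 1 point, well within sampling error, to 5.2 points at a true 15% or 6.7 points at a true 20%. The written selection filters are a separate route by which stoppers can be lost, and a better list would not close it.

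**What to change.** In sections 3.2 and 4.1, define one frame for both centres: every patient with a first prescription or dispensing of raltegravir 600 mg tablets within the initiation window, taken from the centre's prescribing or pharmacy records where these are available and cross-checked against the clinicians' list. Then:

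- order the frame by the initiation prescription date that 3.1 already uses as baseline, and freeze it before outcome data are opened;
- state a single closing date for the window, since 3.1 gives 1 April 2018 and 3.3 gives 30 April 2018;
- remove clinical-trial starters under 3.4, keep a screening log with reasons for non-inclusion, and report starters against included patients by centre;
- reconcile the required-data condition in 3.2, the completed-visit condition in 3.1 and 8.2.1, and the six-months-on-treatment wording in 8.2.1 with the discontinuers expected in 4.1 and the denominator in 8.1.2.

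The cost is one records query per centre, some additional ineligible records to screen, and changes of wording. Where a centre has no searchable prescribing or pharmacy record, the source actually used should be named and its likely gaps stated.

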4.2 Outcomes

The main outcome of this study will be a description of the demographic variables, clinical, and treatment characteristics of people who are initiated on RAL OD in real-life clinical practice in the UK. Virologic and immunologic variables will also be recorded.

4.3 Covariates

Demographic variables at baseline

- Gender: male including trans male/female including trans female. Is this the gender assigned at birth yes/no
- Post-menopausal woman yes/no
- MSM yes/no
- Age
- Ethnicity: White, Black African, Black Caribbean, Black other, Asian, Other/mixed

Virologic variables at baseline and 6 months

- HIV viral load in ART naïve patients
 - Baseline
 - o Continuous (copies/mL): Median (IQR)
 - o Categorical:
 - <1,000 copies/mL

 - \geq 1,000 copies/mL to < 10,000 copies/mL
 - <10,000 copies/mL

 - \geq 10,000 to <100,000 copies/mL
 - $\geq 100,000 \text{ copies/mL}$
 - o 6 month
 - o Continuous (copies/mL): Median (IQR)
 - o Categorical:
 - <50 copies/mL

Protocol/Amendment No.: RETRO STUDY, v0.3

VEAP ID NO: 7651

- 50 to < 200 copies/mL
- 200 to <1,000 copies/mL
- \geq 1,000 copies/mL to < 10,000 copies/mL
- <10,000 copies/mL
- \geq 10,000 to <100,000 copies/mL
- \geq 100,000 copies/mL
- HIV viral load in ART experienced patients at baseline and 6 months
 - o Continuous (copies/mL): Median (IQR)
 - o Categorical:
 - <50 copies/mL
 - 50 to <200 copies/mL
 - 200 to <1,000 copies/mL
 - $\geq 1,000 \text{ copies/mL}$

Immunologic variables at baseline and 6 months

- CD4 cell count and CD4 % in ART naïve and experienced patients
 - o Continuous (cells/mL)
 - o Categorical:
 - > 500 cells/mL
 - >350 to <500 cells/mL
 - >200 to ≤ 350 cells/mL
 - <200 cells/mL

HIV-specific clinical variables at baseline

- RAL OD initiation date
- ART Naïve (yes/no)
- ART experienced (yes/no)
- Prior ART regime if treatment experienced as below (tick box):

NRTI:

- \circ ABC + 3TC
- \circ TDF + FTC
- TAF + FTC

Third agent:

- o dolutegravir
- o atazanavir boosted with ritonavir
- o elvitegravir boosted with cobicistat
- o darunavir boosted with ritonavir
- o raltegravir (400mg bd; other please specify)
- o rilpivirine

Other ART:

o please specify

Protocol/Amendment No.: RETRO STUDY, v0.3

VEAP ID NO: 7651

- Pill burden (number of ART pills)
- AIDS defining illnesses⁹ ever (yes/no)
- AIDS defining illnesses⁹ within the past 6 months (yes/no)

Other Clinical Variables at baseline

- Smoking Status (current, previous, never, unknown)
- Recreational Substance Use (excluding alcohol and tobacco)
- ChemSex (yes/no/unknown)

Comorbidities (Presence of the condition).

- Acid Reflux
- Anaemia
- Anxiety Disorders
- Cancer
- Cardiovascular (any) except hypertension
- Moderate/Severe Chronic kidney disease
- Depression
- Diabetes mellitus
- Hepatitis B
- Hepatitis C
- Hepatitis, Other e.g. alcohol/drug related, autoimmune
- Hepatic Impairment: Child-Pugh or Model for end stage liver disease (MELD)¹⁰
- Hyperlipidaemia
- Hypertension
- Osteopenia
- Osteoporosis
- Schizophrenia/Bipolar or Manic Disorder
- Vitamin D deficiency
- Other co-morbidity

Concomitant non-ARV medications

- lipid-lowering agents
- antihypertensive agents
- anti-inflammatory agents (NSAIDs)
- psychotropic agent (hypnotic, antidepressant and antipsychotic)
- anti-infective agents
- acid suppressants (proton pump inhibitor and H2 antagonist)
- anti-diabetics/insulin
- bone-protecting agents
- methadone

Protocol/Amendment No.: RETRO STUDY, v0.3

VEAP ID NO: 7651

- vitamins, herbal treatment (please specify)
- other prescribed medication (please specify)
- other non-prescribed medication (please specify)

VEAP ID NO: 7651

5 STUDY PROCEDURES

5.1 General Informed Consent

This is a retrospective chart review of RAL OD use among patients at UK centres. As such individual informed consent from subjects will depend on site requirements. Some sites might have a general consent form signed by the patients to stipulate that their data can be used for research. Some other sites might not need informed consent for retrospective chart reviews. Site requirement for informed consent will be documented in the study master filing.

5.2 Data collection

A separate data collection tool will be provided for each centre to enter its patient data. The tool will be structured to prevent the collection, use, or transmission of individual identifiable data. Selected study centres will conduct their own chart review for this purpose – MSD personnel will not come into contact with source data for any patient.

6 Safety Reporting and Related Procedures

This is a non-interventional chart review based on secondary use of data collected for other purposes. No administration of any therapeutic or prophylactic agent is required in this protocol, and there are no additional procedures required as part of this protocol.

6.1 Adverse Event Reporting

6.1.1 INVESTIGATOR RESPONSIBILITY:

Although adverse events are not actively solicited in this study, there are certain circumstances in which individual adverse events will be reported. For example, during review of medical records or physician notes (paper or electronic), to collect data as required by the protocol, if a notation of a serious adverse reaction (SAR), including death, or a non-serious adverse reaction (NSAR) to RAL or any other MSD product is identified, the event must be reported according to Table 1.

Similarly, pre-specified Health Outcomes of Interest (HOIs) that meet criteria for SAR/NSAR, special situations, and any spontaneously reported AEs must be reported according to Table 1.

Protocol/Amendment No.: RETRO STUDY, v0.3

VEAP ID NO: 7651

Table 1: AE Reporting Timeframes and Process for Investigators and Vendors

EVENT TYPE	INVESTIGATOR TIMEFRAMES Investigator to Vendor [1], [2]	VENDOR TIMEFRAMES Vendor to MSD [4]
SAR	24 hours from receipt	1 BD/3 CD
Pre-specified HOI that meets criteria of SAR		(whichever is shorter)
Serious Special Situation, regardless of causality		from time of receipt
		from investigator
NSAR	10 CD from receipt	1 BD/3 CD
Pre-specified HOI that meets criteria of NSAR		(whichever is shorter)
Non-serious Special Situation, regardless of		from time of receipt
causality		from investigator

Spontaneously reported adverse events for MSD products-submit using above timeframes

If the investigator elects to submit AEs for **non-MSD products**, they should be reported to the market authorization holder (MAH) for that product or to the health authority according to the institution's policy or local laws and regulations.

Follow-up to any event-submit using above timeframes

BD-Business Day; CD-Calendar Day

- [1] AE reports from investigators must be transmitted via fax, secure email (if available), or entered directly into vendor's electronic data collection (EDC) platform, if utilized.
- [2] Investigator to Vendor: Applies to events for MSD study product, and other MSD products when a VENDOR is managing AE reporting from investigator to MSD. Events for MSD study product are entered in study database for tabulation in study report. Events for other MSD products are not entered in study database but must be forwarded to MSD via Vendor for regulatory reporting.
- [3] Investigator to MSD: Applies to studies that do not have a vendor managing AEs.
- [4] Vendor to MSD: Applies to events for MSD study product and other MSD products if the vendor is managing AE reporting between investigator and MSD. Not applicable for studies not using a vendor for AE reporting.

Submitting AE reports to Vendor: The Investigator must submit all AEs to the vendor as per the timelines specified in table 1 by fax at [name].

Submitting AE reports to MSD Global Safety: The vendor must submit all AEs as per the timelines mentioned in table 1 by fax to MSD UK Pharmacovigilance Department at [name] or via password protected secure email to [contact], in English using an AE form (attached) for reporting to worldwide regulatory agencies as appropriate.

Protocol/Amendment No.: RETRO STUDY, v0.3

VEAP ID NO: 7651

6.1.2 STUDY REPORT:

The final study report, and any planned interim analysis, will include aggregate listings of all events collected for RAL and will be provided to regulatory agencies by the sponsor as required.

6.1.3 PERIODIC SAFETY UPDATE REPORTS:

Any relevant safety information will be summarized in the appropriate Periodic Safety Update Report (PSUR)/Periodic Benefit Risk Evaluation Report (PBRER) and/or Development Safety Update Reports (DSUR) if required.

6.2 DEFINITIONS

6.2.1 Adverse Event (AE)

Any untoward medical occurrence in a patient or clinical investigation subject administered sponsor's product and which does not necessarily have to have a causal relationship with this product. An adverse event can therefore be any unfavourable and unintended sign (including an abnormal laboratory finding, for example), symptom, or disease temporally associated with the use of the product, whether or not considered related to the product. Any worsening (i.e., any clinically significant adverse change in frequency and/or intensity) of a preexisting condition that is temporally associated with the use of the product, is also an adverse event.

6.2.2 Adverse Reaction (AR); also referred to as Adverse Drug Reaction (ADR)

An AE which has a causal relationship with the product, that is, a causal relationship between the product and the adverse event is at least a reasonable possibility.

6.2.3 Serious Adverse Event (SAE)/Serious Adverse Reaction (SAR)

An adverse event or adverse reaction that results in death, is life threatening, results in persistent or significant disability/incapacity, requires inpatient hospitalization, prolongation of existing inpatient hospitalization, is a congenital anomaly/birth defect, or is another important medical event. Other important medical events that may not result in death, may not be life-threatening, or may not require hospitalization may be considered an SAE/SAR when, based upon appropriate medical judgment, they may jeopardize the patient or subject and may require medical or surgical intervention to prevent one of the other outcomes listed previously. Examples of such medical events include allergic bronchospasm requiring intensive treatment in an emergency room or at home and blood dyscrasias or convulsions that do not result in inpatient hospitalization.

